12.3.2.4 Ivacaftor Exposure

Exposure to ivacaftor (i.e., duration of treatment) will be summarized for the Safety Set in terms of duration of treatment a subject received (in days). Duration of treatment will be summarized by descriptive summary statistics.

12.3.3 Efficacy Analysis

Change (absolute change) from baseline will be calculated as post-baseline value - baseline value. Relative change from baseline will be calculated as (post-baseline value - baseline value)/baseline value.

12.3.4 Safety Analysis

Safety analyses will be based on the Safety Set. All safety data will be presented in individual subject data listings.

12.3.4.1 Adverse Events

All adverse events with start date on or after enrollment date through the last study visit will be summarized. Adverse events are defined in Section 13.1.1. Adverse event summary tables will include the following:

- all adverse events;
- related (identified as related to ivacaftor by the investigator) adverse events;
- adverse events leading to treatment discontinuation;
- serious adverse events (SAEs); and
- adverse events by relationship.

Summaries will be presented by MedDRA system organ class and preferred term using frequency counts and percentages. A subject with multiple occurrences of the same adverse event or a continuing adverse event will be counted only once, by relationship.

12.4 Interim Analyses

No interim analyses will be performed but safety will be monitored throughout.

13 PROCEDURAL, ETHICAL, REGULATORY, AND ADMINISTRATIVE CONSIDERATIONS

13.1 Adverse Event and Serious Adverse Event Documentation and Reporting

13.1.1 Definition of an Adverse Event

For this study, an adverse event is defined as any untoward medical occurrence in a subject during the study, including any newly-occurring event or previous condition that has increased in severity or frequency after the informed consent form is signed.

A subset of adverse events may meet serious criteria. The definition of an SAE and reporting procedures for SAEs are detailed in Section 13.1.2. The definitions below apply to both adverse events and SAEs.

Planned hospital admissions or surgical procedures for an illness or disease that existed before the subject was enrolled in the study are not to be considered adverse events unless the condition deteriorated in an unanticipated manner during the study (e.g., surgery was performed earlier than planned).

13.1.2 Definition of a Serious Adverse Event

An SAE is any adverse event that meets any of the following criteria:

- Fatal (death, regardless of cause, that occurs during participation in the study, or occurs after participation in the study and is suspected of being possibly related to ivacaftor).
- Life-threatening, such that the subject was at immediate risk of death from the reaction as it occurred.

- Inpatient hospitalization or prolongation of hospitalization, with the exception of planned or elective hospitalization.
- Persistent or significant disability/incapacity (disability is defined as a substantial disruption of a person's ability to conduct normal life functions).
- Congenital anomaly or birth defect.
- Important medical event that, based upon appropriate medical judgment, may jeopardize the subject or may require medical or surgical intervention to prevent 1 of the outcomes listed above (e.g., an allergic bronchospasm requiring intensive treatment in an emergency room or at home).

13.1.3 Documentation of Adverse Events

From the time informed consent is signed through the last study visit all adverse events will be collected. The following data should be documented for each adverse event:

- Description of the event
- Classification of "serious" or "not serious"
- Date of first occurrence and date of resolution (if applicable)
- Causal relationship to ivacaftor exposure
- Action taken
- Outcome
- Concomitant medication or other treatment given

For all other adverse events considered related to ivacaftor, see Section 13.1.7.2.

13.1.4 Adverse Event Causality

Every effort should be made by the investigator to assess the relationship of the adverse event, if any, to ivacaftor exposure. Causality should be classified using the categories presented in Table 13-1.

Table 13-1 Classification for Adverse Event Causality		
Classification	Definition	
Related	There is a suspected association between the event and the administration of ivacaftor, a plausible mechanism for the event to be related to ivacaftor and causes other than the ivacaftor have been ruled out, and/or the event reappeared on re-exposure to ivacaftor	
Not related	The event is believed related to an etiology other than the ivacaftor. (The alternative etiology should be documented in the study subject's medical record)	

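### The two causality definitions in Table 13-1 are neither exhaustive nor mutually exclusive, so the related-event tables may undercount or be inconsistent

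*Combined protocol and SAP*

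**What the plan says.** Section 13.1.4 is directive about the scale: "Causality should be classified using the categories presented in Table 13-1". Table 13-1 has two rows.

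- **Related** is built from four elements. The first is suspicion: "There is a suspected association between the event and the administration of ivacaftor". The second is "a plausible mechanism for the event to be related to ivacaftor". The third and fourth are joined by an and/or: "causes other than the ivacaftor have been ruled out, and/or the event reappeared on re-exposure to ivacaftor".
- **Not related** is a positive judgement and not a residual class: "The event is believed related to an etiology other than the ivacaftor". The alternative cause is to be written in the medical record.

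There is no intermediate or unknown class, and no rule for an event that satisfies neither row or both.

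Section 12.3.4.1 plans five adverse event summaries. Two use this classification: "related (identified as related to ivacaftor by the investigator) adverse events" and "adverse events by relationship". The other three cover all events, events that end treatment, and serious events. Section 12.3.4 adds listings of all safety data by subject.

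**The concern.** A two-class scale works only if every event falls in exactly one class. Here the bar for Related is set by exclusion of other causes or by recurrence on re-exposure, and the bar for Not related is set by belief in a specific alternative. The ordinary middle case, where ivacaftor is a credible candidate and so is something else, lies between them.

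That case is easy to foresee in this study. Both subjects have cystic fibrosis, mycobacterial airway infection is of particular interest, and Section 9.1 intends antibiotics if the infection persists. Other causes will often be hard to exclude. Table 3-1 schedules no re-exposure, which would arise only if dosing happened to be interrupted and resumed (an interruption is one of the actions in Table 13-2). There is no comparator, so attribution to ivacaftor in the planned summaries rests on the investigator's classification.

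At stake are two of the five event summaries, in a study whose objective (Section 7) names safety beside efficacy.

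**Working it through.** The plan states no figure on this point, so there is none to reproduce. The check is logical: list the possible patterns of evidence and apply Table 13-1 to each.

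**Inputs, all from Table 13-1.** A = association suspected. B = mechanism plausible. C = other causes ruled out. D = recurred on re-exposure. E = investigator believes another cause is responsible. Not related = E.

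**Patterns.** Five yes/no elements give 2^5 = 32 patterns. C and E together are contradictory, which removes 2^3 = 8 and leaves 32 - 8 = 24. Of these, 6 have both A and B true. Of those 6, 4 have E false: the investigator suspects ivacaftor, finds it plausible, and does not hold another cause responsible.

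**Readings of the and/or.**
1. Related = (A and B and C) or D.
2. Related = A and B and (C or D).
3. Loose reading: Related = any one of A, B, C, D.

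**Result for the four patterns with A and B true and E false:**

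| C: others ruled out | D: recurred | Reading 1 | Reading 2 | Reading 3 |
|---|---|---|---|---|
| no | no | neither class | neither class | Related |
| no | yes | Related | Related | Related |
| yes | no | Related | Related | Related |
| yes | yes | Related | Related | Related |

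Under both natural readings, three of the four patterns are Related and one has no class. The gap closes only under reading 3. That reading does not fit the wording, because bare suspicion, or ruling out other causes without any suspicion of ivacaftor, would then be enough.

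**Overlap.** With E true, C must be false. Patterns that meet both rows number 4 under reading 1 (D true, A and B free: 2 x 2) and 1 under reading 2 (A, B and D all true). Under reading 3 there are 7 (any of A, B, D true: 2^3 - 1). So the reading that closes the gap makes the overlap worse.

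**Comparison with another part of the protocol.** The additional reporting procedures (Section 13.1.7.1) encourage reports to the FDA on suspicion that ivacaftor is the cause, with no need to exclude other causes. In Table 13-1 suspicion alone is not enough. The same event could therefore be reported as a suspected reaction and yet fail the definition of Related in the study's own summaries.

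**Effect on the tables.** Section 12.3.4.1 counts a subject once for repeat occurrences of the same event, by relationship. With two subjects, a count for one event term is 0, 1 or 2. If a subject has no other occurrence of that term classed as Related, one reclassification moves the entry by 1/2, or 50 percentage points. How many events would be affected cannot be computed from the documents.

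**The case against.** The strongest reply is that a gap in definitions does not establish an undercount. An investigator who suspects ivacaftor and believes in no other cause does not meet Not related either, and might sensibly record the event as Related. That stands. A reader might infer that the error can run only one way and make ivacaftor look safer than it is. The documents do not support this, because they do not say where an unclassifiable event goes. For the same reason, any percentage of related events lost would only restate an assumed share.

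Second, the harm is bounded. The all-events summary, the SAE summary and the summary of events that end treatment do not use Table 13-1. Section 13.1.3 has each event documented with description, dates, action, outcome and treatment given, and the listings cover both subjects in full, so a reader can judge each event afresh. With only two classes, the by-relationship table largely repeats the related table. The IRB reporting clause in Section 13.1.7 applies whatever the causality. All of this stands, and it lowers the severity. It does not repair the classification that the two tables will show.

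Third, a reader might take the wording in Section 13.1.2, "is suspected of being possibly related to ivacaftor", as proof that a class for possible relationship was intended and left out. It is not. The phrase decides only whether a death after participation counts as an SAE. It does not grade the events collected in the study, and that section needs no edit.

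**Conclusion.** The point holds as a defect of definition, and it is minor. Under either natural reading of the and/or, a suspected and plausible event with other causes not excluded, no recurrence on re-exposure and no belief in another cause has no class. An event that recurs on re-exposure but is believed due to another cause can have two. Nothing else in the documents supplies a default. Section 12.3 leaves analysis details to a SAP to be finalized before database lock, but the class is assigned event by event by the investigator, so a later analysis rule would come after the judgement.

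If the text is applied literally, the first kind of event is kept out of Related, and the related and by-relationship tables may then undercount. If investigators depart from the text, those tables may be inconsistent. Which of these happens, and how often, is unknown. The conclusion rests only on the wording of Table 13-1 and on its use in Section 12.3.4.1, with no assumption about event rates.

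**What to change.** Reword the two rows of Table 13-1 and the matching CRF text:

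- **Related:** there is a reasonable possibility that ivacaftor caused or contributed to the event. Other causes need not be excluded.
- **Not related:** another etiology is documented, and there is no reasonable possibility that ivacaftor contributed.
- **Default:** an event that clearly meets neither definition is counted as Related.

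The two rows can then no longer both apply, and the default makes the scale exhaustive. It also brings Table 13-1 into line with the suspicion threshold in the additional reporting procedures. A third class with its own tabulation rule would also close the gap, but the two-row version leaves the planned tables unchanged.

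The cost is one table edit and one CRF edit, with no change to visits, treatment or sample size. The downside is that a few more events will be counted as related, including some unexplained events that reach that class only through the default.

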13.1.5 Action Taken with Ivacaftor

The investigator will classify the action taken with regard to ivacaftor due to the adverse event. The action taken should be classified according to the categories shown in Table 13-2.

Table 13-2 Classification for Ivacaftor Action Taken With Regard to an Adverse Event		
Classification Definition		
Dose Not Changed	Ivacaftor treatment not changed in response to an adverse event	
Drug Interrupted	Ivacaftor administration interrupted in response to an adverse event	
Drug Withdrawn	Ivacaftor administration permanently discontinued in response to an adverse event	
Not Applicable	Action taken regarding ivacaftor administration does not apply. "Not applicable" should be used in circumstances such as when the ivacaftor	

	treatment had been completed before the adverse event began and no opportunity to decide whether to continue, interrupt, or withdraw treatment is
	possible

13.1.6 Adverse Event Outcome

An adverse event should be followed until the investigator has determined and provided the final outcome. The outcome should be classified according to the categories shown in Table 13-3.

Table 13-3 Classifications for Outcome of an Adverse Event		
Classification	Definition	
Recovered/Resolved	Resolution of an adverse event with no residual signs or symptoms	
Recovered/Resolved with Sequelae	Resolution of an adverse event with residual signs or symptoms	
Not Recovered/Not resolved (Continuing)	Either incomplete improvement or no improvement of an adverse event, such that it remains ongoing	
Fatal	Outcome of an adverse event is death. "Fatal" should be used when death is at least possibly related to the adverse event	
Unknown	Outcome of an adverse event is not known (e.g., a subject lost to follow-up).	

13.1.7 Reporting Procedure for Adverse Events and Pregnancy

All serious and non-serious vision-related events (as defined in Section 13.1.1) that occur after obtaining informed consent and assent (where applicable) through the last study visit, regardless of causality, must be reported to the MUSC IRB within 24 hours of their awareness.

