2 PROTOCOL SYNOPSIS

T			
Title	An Efficacy and Safety Study of Ivacaftor in Patients With Cystic Fibrosis		
	and Splicing Mutations		
Clinical Phase	N of 2 Study		
Objective	To evaluate the efficacy and safety of ivacaftor in two patients (sisters)		
	who have a splicing mutation and pancreatic sufficiency		
Endpoints	Primary		
	Absolute change in percent predicted forced expiratory volume in		
	1 second (FEV ₁) from baseline through Week 24		
	Key Secondary		
	Relative change in percent predicted FEV1 from baseline through		
	Week 24		
	Achievement of mycobacterial culture conversion (negative		
	culture) by Week 24		
	 Secondary Safety and tolerability assessments based on adverse events (AEs), 		
	clinical laboratory values (i.e., liver function tests)		
	Absolute change in sweat chloride from baseline through Week 24		
	Absolute change in respiratory symptom scores from baseline at		
	Week 24		
Study	Sisters with specific mutations		
Population			
Number of	2		
Subjects			
Study	Subjects will be treated for 6 months and followed for 7 months		
Duration			
Study Design	This postmarketing N of 2 study is designed to evaluate the efficacy and		
	safety of open-label ivacaftor treatment in two sisters with cystic fibrosis		
	and pancreatic sufficiency. They have a splicing mutation that is predicted		
	to respond favorably to ivacaftor therapy. In addition to measurement of		
	usual clinical outcomes (i.e. lung function, nutritional status), there is great		
	interest on the impact on nontuberculous mycobacteria (NTM) airways		
	infection.		
	Subjects will undergo sputum cultures at baseline and monthly during		
	treatment, initially in the absence of anti-NTM therapy but with the intent		
	to treat with antibiotics if there is persistence of the infection in cultures.		
	Other clinical outcomes will include changes in sweat chloride, lung		
	function and weight. Safety measures will include periodic assessment of		
Assessments	liver enzymes. All serious and non-serious adverse events will be collected		
Assessifients	Efficacy: spirometry, sweat chloride testing, CRISS, sputum cultures		
	(bacteria and mycobacteria), height, and weight Safety: AEs, clinical laboratory assessments (liver function tests), vital		
	signs, physical examinations, and pulse oximetry		
Statistical	Statistical analysis details will be provided in the Statistical Analysis Plan		
Analyses	(SAP), which will be finalized before the clinical data lock for the study.		

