3 SCHEDULE OF ASSESSMENTS

The Schedule of Assessments is shown in Table 3-1

	Visit 1	Visit 2	Visit 3	Visit 4	Visit 5	Visit 6	Visit 7	Visit 8
Event/Assessment	Day 1	Day 30	Day 60	Day 90	Day 120	Day 150	Day 180	Day 210
Informed consent	X							
Medical history	х							
Demographics ^a	х							
Physical examination	Х	×	×	х	x	×	×	х
Height and weight	х	х	х	х	х	х	х	х
Sweat test	х	х		х			х	х
Spirometry	х	х	х	х	х	х	х	х
Genetic testing ^b	х							
Liver function tests ^c	х			х			х	
Sputum cultures ^d	х	х	х	х	х	х	х	х
CRISS	Х	Х	Х	х	х	Х	Х	х
Adverse events		Х	Х	х	х	Х	х	х
Concomitant medications	х	х	х	х	х	х	х	х
Study drug dispensed	х	х	х	х	х	х		

Demographics include sex, race, and age. Baseline characteristics include age at CF diagnosis, CFTR genotype Genetic testing will get confirm that the two mutations are not on the same allele (with a cryptic additional mild mutation on the other allele)._

Safety labs include liver enzymes (ALT, AST, GGT)_
Sputum will be tested for bacteria and mycobacteria (including AFB smear and culture). Susceptibility testing will not be performed

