13.1.7.1 Additional Adverse Event Reporting Procedures

Investigators are encouraged to report any adverse reactions suspected due to ivacaftor to the FDA at [name] or www.fda.gov/medwatch.

Investigators should also report any suspected adverse reactions related to ivacaftor, other than those being collected as part of the study, as well any pregnancies, to Vertex Pharmaceuticals Incorporated at [name].

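### The only mandatory, time-limited reporting rule (Section 13.1.7) covers vision-related events, which Section 13.1.1 does not define, so as worded a non-ocular SAE triggers no 24-hour IRB report

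*Combined protocol and SAP*

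**What the plan says.** Section 13.1.7 requires "All serious and non-serious vision-related events (as defined in Section 13.1.1") to be reported to the IRB within 24 hours of awareness, regardless of causality, from consent to the last study visit.

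Section 13.1.1 gives a general definition of an adverse event. On serious events it says: "The definition of an SAE and reporting procedures for SAEs are detailed in Section 13.1.2". Section 13.1.2 opens with "An SAE is any adverse event that meets any of the following criteria" and then lists the criteria.

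Section 13.1.3 has all adverse events collected and documented. For other events judged related to ivacaftor, it points to Section 13.1.7.2. The body has no section of that number; the additional reporting procedures are printed as 13.1.7.1. There, "Investigators are encouraged to report any adverse reactions suspected due to ivacaftor to the FDA". The same section says that investigators should report to Vertex any pregnancies and "any suspected adverse reactions related to ivacaftor, other than those being collected as part of the study".

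The synopsis lists the safety assessments as "AEs, clinical laboratory assessments (liver function tests), vital" signs, physical examinations and pulse oximetry. The footnote to Table 3-1 reads "Safety labs include liver enzymes (ALT, AST, GGT").

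**The concern.** The word vision-related qualifies events, and so limits both the serious and the non-serious ones. The one rule with a firm duty and a deadline then covers a class of events that the study does not set out to measure and that the cited section does not define. It leaves out most of what 13.1.2 calls serious.

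At stake is how soon the IRB hears of a serious event. Treatment is open-label, the investigator analyses the data (Section 12) and writes the report (13.5.2), and no interim analysis is planned (12.4). The IRB is the body charged in 13.2.1 with safeguarding the subjects, and 13.1.7 is the only provision that gives it event information by a deadline.

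**Working it through.** No arithmetic applies. The check sets every reporting provision side by side.

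| Section | Trigger | Strength | Recipient | Time limit |
|---|---|---|---|---|
| 13.1.1 | None; defines adverse events and refers SAE reporting to 13.1.2 | – | – | – |
| 13.1.2 | None; seriousness criteria only | – | – | – |
| 13.1.3 | All adverse events | Collected and documented | Study record | – |
| 13.1.7 | Vision-related events, serious or not | Must | IRB | 24 hours |
| 13.1.7.1 (FDA) | Reactions suspected due to ivacaftor | Encouraged | FDA | None |
| 13.1.7.1 (Vertex) | Suspected related reactions other than those collected in the study; pregnancies | Should | Vertex | None |
| 13.5.2 | Study report | Will be written and submitted | Vertex, then FDA | None |

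The available text therefore has one mandatory, timed rule. It has no definition of vision-related, no reporting step in 13.1.2, and no 24-hour rule that names SAEs without the vision qualifier.

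Applying the plain wording to each class of event gives:

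| Event | 24-hour IRB report | Other stated outward route before the study report |
|---|---|---|
| Vision-related, serious or not | Yes | FDA or Vertex if suspected related, untimed |
| Non-ocular SAE, related | No | Arguably FDA or Vertex through 13.1.3, untimed |
| Non-ocular SAE, unrelated | No | None |
| Non-ocular, non-serious | No | As for the SAE rows, by relatedness |

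Two features suggest that the limit is leftover wording. First, none of the planned safety assessments in the synopsis or Table 3-1 is ocular, and the only scheduled safety laboratory tests are liver enzymes. Second, the same sentence of 13.1.7 provides for assent where applicable, although Section 10.1 requires both subjects to be over 18.

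The numbering is also broken. The contents list 13.1.7.1 as the reporting procedure and 13.1.7.2 as the additional procedures, and 13.1.3 agrees with them. The body lacks the first of these headings and prints the additional procedures as 13.1.7.1.

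**The case against.** The best case for the plan is that a wider scope was meant. The heading of 13.1.7 speaks of adverse events without restriction. The section it cites holds the general definition, and that section adds: "The definitions below apply to both adverse events and SAEs". This stands as evidence of intent, but it does not override the operative sentence. Dropping the qualifier altogether would put every non-serious event under a 24-hour duty. Dropping it for serious events alone would give another scope again. The text does not choose between them.

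A second argument is that 13.1.3 supplies a back-up. It sends other related events to the additional procedures, and the Vertex exclusion may remove only events already under the 24-hour rule. This is a fair reading, so it would be too strong to say that non-ocular SAEs have no outward route. But the route is untimed, does not reach the IRB, and does not cover SAEs judged unrelated.

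Third, Section 13.2.1 commits the study to local laws and regulations and gives the IRB a review role. Such rules may well require prompt SAE reports. Their content is not stated, so they neither close the gap nor allow the conclusion that no SAE duty exists.

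Finally, the consequence is narrow: events are collected (13.1.3), listed and summarised (12.3.4 and 12.3.4.1), and safety is to be monitored throughout (12.4). That is correct, and it limits the point without removing it.

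**Conclusion.** The point holds on the text. Followed as written, 13.1.7 gives the 24-hour rule a trigger that leaves out non-ocular SAEs, and no other section states an equivalent duty to the IRB. This is more than a clerical slip, because it sits in an operative safety rule. Its consequence is limited to prompt IRB oversight in two subjects; no endpoint or efficacy analysis is affected.

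A reader might infer more, but the documents do not support it:

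- **That serious events would be lost or reported to no one.** All adverse events are recorded, and related ones arguably have an untimed route.
- **That the length of the delay can be stated.** The study report has no date and goes to Vertex and the FDA, so it is no measure of when the IRB would learn of an event.
- **That the intended scope is proven.** The signs of leftover wording are suggestive only. Table 3-1 is not a complete list of safety assessments, since vital signs and pulse oximetry have no row of their own. The cataract entries in the reference list add little, because part of the introduction was not available and might cite them.

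The conclusion assumes that the unavailable text, which lies before the synopsis and in the introduction, holds no reporting rule.

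**What to change.** Reconcile Sections 13.1.1, 13.1.2, 13.1.3, 13.1.7 and 13.1.7.1:

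1. Reword 13.1.7 so that the 24-hour IRB rule expressly covers all serious adverse events as defined in Section 13.1.2, regardless of causality.
2. State whether non-serious vision-related events, and other non-serious events, are also under the rule, so that neither class is dropped silently. Define vision-related if the term is kept.
3. Clarify which reactions the exclusion in the Vertex route removes.
4. Point 13.1.1 to 13.1.7 for SAE reporting. Restore the missing body heading for 13.1.7.1 (the reporting procedure), so that the additional procedures become 13.1.7.2, as the contents and 13.1.3 already have it.

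The cost is one wording amendment, which 13.2.3 requires the IRB to approve, and at most a few more expedited reports from two subjects at one site. No assessment, visit or analysis changes.
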